
The proposed work will test key predictions of the FMDM account of CM with implications for (1) improved treatment effectiveness and (2) targeted treatment delivery. Individuals with CUD (n=140) will be recruited upon engagement with outpatient substance use services and assigned to 12 weeks of TangiblePBCM (n=70) or VoucherPBCM (n=70). Participants in all conditions will complete EEG and cognitive-behavioral assessments of core FMDM constructs (i.e., goal-informed cognitive control processes, executive working memory, episodic future thinking, and reward anticipation) before and after the 12 week treatment interval. Self-report measures of other clinically-relevant indicators (e.g., addiction propensity and severity, motivation, self-efficacy) will also be evaluated and outcomes (treatment engagement, subjective and objective measures of substance use) will additionally be

followed throughout the 12 week treatment interval and for 6 months post-treatment in both CM groups. Aims and hypotheses are as follows:

Specific Aim 1: Evaluate the utility of EEG and cognitive-behavioral measures of FMDM as predictors of differential treatment outcomes in TangiblePBCM versus VoucherPBCM.

Hypothesis 1a. FMDM-related measures will predict differential outcomes in TangiblePBCM relative to VoucherPBCM, with more FMDM-impaired individuals demonstrating improved treatment response in the former relative to the latter.

Hypothesis 1b. Inclusion of predictors from the FMDM account will significantly improve performance of predictive models forecasting short- and long-term outcomes in CM and inclusion of these predictors will be robust to model-based constraints favoring variables with lower measurement costs.

Specific Aim 2: Evaluate treatment-related change in EEG and cognitive-behavioral correlates of FMDM-related cognitive functioning during CM.

Hypothesis 2a. Individuals who reliably engage in TangiblePBCM and VoucherPBCM will demonstrate greater treatment-related change in functional connectivity networks underlying goal-informed cognitive control processes, as well as behavioral measures of working memory and future-oriented decision-making, relative to individuals who demonstrate poor PBCM adherence.

Exploratory Sub-Aim. Longitudinal change in FMDM-related measures will be investigated in relation to patterns of abstinence during PBCM and will reflect distinct treatment response trajectories.

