To address limitations related to the ratio of observations to predictors in the context of our reduced sample size, we revised our predictive analytic approach (Specific Aim 1) to prioritize model stability and interpretability, while framing results as more preliminary in nature. With respect to Aim 1, a revised sample size of ~50 participants was identified as sufficient to support investigation of up to five candidate predictors: e.g., two EEG-derived metrics, one clinical measure, one neurocognitive measure, and treatment condition. Recent simulation-based work (Austin & Steyerberg, 2015) further suggests that as few as two participants per predictor may be adequate, supporting investigation of the original candidate set even within the reduced sample. Two consulting biostatisticians endorsed this revised approach and further recommended modeling repeated binary outcomes over the course of CM treatment to improve power. In line with this recommendation, we modeled 24 repeated binary outcomes per participant, yielding up to $24 \times n$ observations across n participants. However, recognizing that the effective number of independent events remains tied to the number of participants rather than the number of observations, we adopted a two-stage variable selection process to reduce the risk of overfitting. In the first stage, we screened predictors using single-predictor longitudinal logistic regression models, identifying those with theoretically plausible associations with the outcome. This process narrowed our total number of candidate predictors. In the second stage, we applied stepwise forward selection guided by the Akaike Information Criterion (AIC) to construct a parsimonious, interpretable multivariate model. To further assess model robustness and generalizability, we evaluated predictive performance using leave-one-out cross-validation (LOOCV).

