of FMDM function (i.e., EEG and cognitive-behavioral measures) is hypothesized. Specifically, individuals demonstrating greater FMDM impairment (poorer working memory function, less reduction in delay discounting with inclusion of future event tags, and reduced EEG/ERP signaling to abstract future reward and control demands) will achieve better outcomes in Tangible PBCM, relative to VoucherPBCM (Hypothesis 1a). In models including PBCM treatment condition as a factor, inclusion of EEG and cognitive-behavioral predictors is expected to significantly reduce prediction error with respect to both PBCM treatment response and long-term outcomes. Differential alpha suppression in response to tangible prize versus voucher prize rewards, in particular, will assay engagement by different types of future reward utilized in TangiblePBCM and VoucherPBCM. Consequently, differential alpha suppression is expected to be an especially robust predictor of outcomes in existing PBCM variants. It is further hypothesized that this candidate biomarker will be selected for inclusion in a readily translatable predictive model – even when incorporating resource constraints that penalize predictors derived from more costly procedures (e.g., EEG incurring a greater cost-based penalty than self-report measures; Hypothesis 1b).

The proposed design affords measurement of all candidate predictors prior to initiation of PBCM, as well as monitoring of both CM treatment response and long-term outcomes for all CM recipients. Predictive models of CM treatment response and long-term outcomes will be developed separately, with the caveat that our revised final sample size may not support the latter. Candidate predictors will include pretreatment FMDM-related EEG (concrete versus abstract alpha suppression, ERN amplitude, parametric N2 amplitude effect) and cognitive-behavioral measures (Brown-Peterson score, $\Delta \ln(k)$), as well as clinical indicators (e.g., craving severity, past month cocaine use, number of previous treatment episodes) and self-report scores. In order to examine the interaction between candidate predictors and CM reward parameters, PBCM condition (TangiblePBCM versus VoucherPBCM) will also be considered as an explanatory variable in predictive models.

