I will receive focused training in predictive modeling, with an emphasis on recursive partitioning machine learning methods: classification and regression trees (CART) and random forests (RF). Our original analytic plan proposed that regression trees would be grown to examine the predictive structure of explanatory variables (including PBCM treatment condition) with respect to the following continuous outcomes: (1) % cocaine-negative urines during CM, (2) % CM sessions attended, (3) % days of any self-reported substance use during CM, and (4) % days of self-reported stimulant use during the 6 months following CM. CART involves partitioning observations into more homogenous subgroups with respect to the outcome of interest by identifying cut points along predictor variables. For each CART, cost-complexity pruning would be conducted using five-fold cross validation to limit overfitting. A Random Forest (RF) approach would subsequently be implemented with each set of predictors and outcomes to objectively evaluate the relative importance of each predictor and optimize overall model performance. RF involves growing an ensemble of decision trees based on bootstrapped samples of observations and predictors to increase tree diversity. This method includes internal cross-validation using out-of-bag error rates (based on observations not included in the bootstrap sample) to limit overfitting during model training and performs well without excessive tuning of model parameters. Taken together these data mining approaches would provide deep insight into interrelationships between predictors and outcomes of interest and could also be further examined through a resource-constrained Tabu search procedure to develop multiple regression models forecasting treatment response (% cocaine-negative urines) in each PBCM variant, while penalizing individual predictors based

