on measurement cost.¹⁰³ Resource-constrained Tabu search has not previously been used to analyze the predictive utility of neuromarkers in view of the increased cost of measuring these signals but is ideally suited to this issue in measurement-based care. In our revised approach, we employed longitudinal logistic regression as described above and specifically examined outcomes on a per session basis, with provision of a cocaine-negative specimen at the session being considered a successful outcome and cocaine-positive or missing specimens considered unsuccessful. This revised approach enables more efficient use of the available data by capturing the full trajectory of participant responses over time through repeated measures modeling, rather than relying on a single aggregated outcome.

Missing Data Strategies: Recursive partitioning approaches (CART, RF) flexibly handle missing data for candidate predictors through several heuristic and/or interpolation based approaches. Missing data handling for TABU search is not yet well-characterized but works well, provided that missing data is randomly distributed and relatively rare. Expecting a 15% rate of attrition, usable substance use outcome data is anticipated for a minimal sample size of $n = 119$ CM recipients. Additional outcome variables will be derived from chart review (e.g., treatment engagement, urinalysis results), providing additional options for quantifying outcomes, not contingent on participation in study check-in appointments. Importantly, all methods specified above can be used with binary outcomes (i.e., CM-completer versus CM-non-completer). Consequently, while efforts will be made to collect detailed outcome data on each participant (and this appears feasible on the basis of my ongoing pilot project), primary predictive modeling aims can be accomplished under circumstances of high attrition and data loss. Our revised analytic approach has also been configured to be resilient to missingness through handling missing specimens as unsuccessful outcomes using an intent-to-treat approach. Where necessary (e.g., for treatment trajectories impacted by the pandemic), a Bayesian logistic regression model can also be used to impute missing values based on observed patterns to estimate likely values for unobserved responses.

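### Hypothesis 1b still claims that the EEG marker survives a measurement-cost penalty, but the revised Aim 1 analysis has no cost term, so no planned result can support that clause

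*Combined protocol and SAP*

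**What the plan says.** The cost clause stands in two places. In the study objectives (Study Summary, item 3.0), Hypothesis 1b says that "inclusion of these predictors will be robust to model-based constraints favoring variables with lower measurement costs". In section 4.1 (analysis plan), under Specific Aim 1, the prediction is narrowed to differential alpha suppression: "this candidate biomarker will be selected for inclusion in a readily translatable predictive model", and this is to hold "even when incorporating resource constraints that penalize predictors derived from more costly procedures". EEG is given there as an example of a measure that would be penalised more heavily than self-report. No amounts are stated.

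The method that carried a cost penalty appears later under Specific Aim 1, in text that opens "Our original analytic plan proposed that regression trees would be grown". After the tree and forest steps, the relationships "could also be further examined through a resource-constrained Tabu search procedure".

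The revised method is described in two parts of section 4.1. Under Power Analysis and Sample Size: "we screened predictors using single-predictor longitudinal logistic regression models", and then "we applied stepwise forward selection guided by the Akaike Information Criterion (AIC) to construct a parsimonious, interpretable multivariate model", followed by leave-one-out cross-validation. Under Specific Aim 1: "In our revised approach, we employed longitudinal logistic regression as described above", with a binary outcome at each session.

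**The concern.** The analysis was replaced and the hypothesis that depended on it was not. The same part of Specific Aim 1 was edited for the smaller sample, since the long-term models now carry a warning that they may not be feasible. The cost clause has no such warning, so a reader will take it as live.

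The clause separates two conclusions: that an EEG measure predicts response, and that it still earns its place once its expense is counted. The plan itself presents the second as an issue for measurement-based care. If alpha suppression enters the AIC model, Hypothesis 1b could be reported as supported in full although the cost condition was never applied.

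**Working it through.** No figure in the plan bears on this point, so there is none to reproduce. The check sets hypothesis against method and then illustrates how far apart the two selection rules lie.

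**1. Where a cost term appears**

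| Element | Status | Cost term? |
|---|---|---|
| Hypothesis 1b, objectives | current, no caveat | required |
| Hypothesis 1b, Specific Aim 1 | current, no caveat | required |
| Resource-constrained Tabu search | original plan, optional | yes |
| One-at-a-time screening | revised plan | no |
| Forward selection by AIC | revised plan | no |
| Leave-one-out cross-validation | revised plan | no (measures prediction) |
| Tabu remark under Aim 1 Missing Data Strategies | leftover | schedules no analysis |
| Closing allowance for further analyses, section 4.1 | open-ended | names no cost analysis |

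**2. What AIC charges**

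AIC = −2 log L + 2k. Adding a one-parameter term lowers AIC when its likelihood ratio LR exceeds 2. The measurement cost of the predictor does not enter.

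Suppose instead that the penalty were 2 × Σc_j, where c_j is relative cost and self-report has c = 1. An EEG term would then need LR > 2c. The values of c below are assumptions.

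| c | Entry rule | Equivalent p (chi-square, 1 df) |
|---|---|---|
| 1 (plain AIC) | LR > 2 | 0.157 |
| 1.5 | LR > 3 | 0.083 |
| 2 | LR > 4 | 0.046 |
| 3 | LR > 6 | 0.014 |
| 5 | LR > 10 | 0.0016 |

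**3. Does passing plain AIC imply passing the cost rule?**

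Take one real predictor with noncentrality 4 (assumed). The chance of passing the cost rule, given that plain AIC admits the term, is P(LR > 2c) / P(LR > 2):

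- c = 1.5: 84%
- c = 2: 69%
- c = 3: 45%
- c = 5: 17%

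**4. The same question in a full forward selection**

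This was a simulation with 50 participants, five mildly correlated predictors, a linear model for simplicity, and coefficients of 0.3 on the marker and on one other predictor (all assumed except the 50 and the five). There were 1500 data sets per cost ratio.

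| c | Selected, plain AIC | Selected, cost-weighted | Retained, given plain selection |
|---|---|---|---|
| 1.5 | 81% | 70% | 86% |
| 2 | 80% | 60% | 75% |
| 3 | 78% | 41% | 53% |

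In none of the 1500 data sets at any c did the cost-weighted run select the marker when plain AIC had left it out.

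**5. Reading**

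Selection under plain AIC does not establish survival under a cost penalty. The reverse is different: a marker that fails the lenient rule is very unlikely to pass the stricter one, so non-selection does carry information.

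**The case against.** Several points on the other side stand, and they limit the conclusion.

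- **The cost search was never firm.** It was optional in the original plan, so a reader who infers that a committed test was removed would be wrong. Dropping it at about 50 participants was also reasonable. What remains is a hypothesis left without any test.
- **It is tempting to say that nothing planned can bear on the clause either way.** That goes too far, because non-selection under plain AIC would count against it indirectly.
- **It is tempting to call the whole of Hypothesis 1b untestable.** The documents do not support that. AIC and cross-validation can still address improved prediction for short-term response. The long-term part already carries the plan's own caveat.
- **A reader might take 15.7% as the false-selection rate of the trial's procedure.** It is the generic entry rate for one uninformative term tested alone. It ignores the screening stage, which has no numeric threshold, and competition between predictors. It also ignores the marker-by-condition interactions, and it presumes a proper likelihood for the 24 correlated outcomes per participant.
- **A reader might infer that translation to practice rests on this clause.** The plan grounds translation mainly in both incentive versions already being used in VA clinics, and none of the recommendations in its Table 1 depends on measurement cost.
- **The revised results are framed as preliminary, and further analyses are allowed.** Both are true. Neither specifies a test of a named hypothesis, and neither does the leftover Tabu remark.

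**Conclusion.** The point holds for the cost clause only. Hypothesis 1b keeps that clause without caveat in the objectives and in Specific Aim 1, the only cost-penalised method belongs to the superseded plan, and the revised procedure treats cheap and costly predictors alike. No planned result can support the clause.

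This conclusion rests on the text and needs no numerical assumption. The figures only show that the gap is not trivial: at cost ratios of 1.5 to 3, between 86% and 53% of plain-AIC selections survived in the simulation. They depend on assumed cost ratios and effects and do not estimate what this trial would find.

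No participant or outcome measurement is affected. What changes is what the trial may conclude about Hypothesis 1b.

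**What to change.** **Preferred.** State beside Hypothesis 1b, in the objectives and in Specific Aim 1, that the cost-robustness clause is not tested under the revised plan and will not be reported as supported because AIC selects the marker. Remove the leftover Tabu sentence from the Aim 1 Missing Data Strategies. This costs a few lines of wording, and the clause is given up.

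**Alternative.** Add a cost-weighted rerun of the forward selection on the existing data. The plan reports the revised selection in the past tense, so the rerun cannot be presented as pre-specified and must be labelled post hoc and exploratory. It needs:

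- cost weights stated for every class of predictor: EEG, cognitive task, self-report, treatment condition and interaction terms;
- results shown over the whole range of weights, not at one chosen value;
- robustness claimed only for the cost ratios at which the marker is retained.

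This is a short rerun plus wording. The downside is that the EEG marker may drop out at the higher cost ratios.
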